6.2 Protocol Therapy Discontinuation

In addition to discontinuation from therapy related to toxicities as outlined in Section 6.1, a subject will also be discontinued from protocol therapy and followed up per protocol under the following circumstances:

- Evidence of disease progression
- The treating physician thinks a change of therapy would be in the best interest of the subject
- The subject requests to discontinue protocol therapy, whether due to unacceptable toxicity or for other reasons
- In case a subject decides to prematurely discontinue protocol therapy (“refuses treatment”), the subject should be asked if she or he may still be contacted for further scheduled study assessments. The outcome of that discussion should be documented in both the medical records and in the eCRF.
- A female subject becomes pregnant
- Delays of greater than 4 weeks are prohibited without approval of the Sponsor.

Subjects will be removed from protocol therapy and the site investigator notified when any of the criteria listed above apply. The reason for discontinuation of protocol therapy will be documented on the electronic case report form (eCRF).

6.3 Study Withdrawal

If a subject decides to withdraw from the study (and not just from protocol therapy) all efforts should be made to complete and report study assessments as thoroughly as possible. The treating investigator should contact the subject or a responsible relative by telephone or through a personal visit to establish as completely as possible the reason for the study withdrawal. A complete final evaluation at the time of the subject’s study withdrawal should be made with an explanation of why the subject is withdrawing from the study. If the reason for removal of a subject from the study is an adverse event, it will be recorded on the eCRF.

7. STUDY CALENDAR & EVALUATIONS

Procedure	Screening ¹ (≤ 28 days before 1 st dose)	Every Cycle (21 days ± 3 days)	Before cycle 3 & cycle 5	Before cycle 9 & then after every 4 cycles	Post Treatment Safety Assessments ⁶	Follow-Up ¹⁰
Informed consent and medical history	X					
Patient Registration	X					
Brentuximab vedotin administration ²		X				
ECOG Performance Status	X	X			X	
Physical exam ³ , vital signs	X	X			X	
Serum AFP and beta-hCG	X	X			X	X ¹²
CBC (differential & platelets)	X	X ^{4,11}			X	
Complete metabolic panel	X	X ⁴			X	
Magnesium and phosphorus	X	X ⁴			X	
Pregnancy test ⁵	X	X			X	
Concomitant medications	X	X			X	
Adverse event monitoring ⁷		X			X	
Radiologic evaluations ⁸	X		X	X		X ¹²
Archival tissue ⁹	X					
Survival						X

Footnotes:

- 1 All procedures are to be performed ≤ 28 days prior to study drug administration. Screening assessments may be used in place of the Cycle 1 Day 1 assessments if performed within 7 days prior to the Day 1 visit. Standard of care procedures may be used for screening requirements if performed within 28 days prior to study drug administration.
- 2 Brentuximab vedotin is administered on Day 1 of each Cycle. First dose must be administered within 7 days of registration.
- 3 Complete physical exam to be performed within 28 days of first study drug administration (for screening requirements), Day 1 Cycle 1 and at Final Safety Follow-up. At other time-points, a brief symptom-directed exam and ECOG performance evaluation are sufficient. At Screening, height is recorded and body surface area (BSA) calculated
- 4 Hematologic and chemistry parameters (including serum creatinine, AST, ALT, BUN, phosphate, bilirubin, calcium & magnesium) to be performed on Day -3 to Day 1 of every cycle.
- 5 Females of childbearing potential only. Pregnancy tests must be serum at screening and the post treatment safety assessment visit. Urine pregnancy tests are required on Day 1 of each Cycle. A positive urine pregnancy test must be confirmed by a serum pregnancy test and a pelvic US since some NSGCT can secrete beta-hCG. A pelvic US does not need to be repeated with each cycle unless the treating physician thinks it is necessary to do so.
- 6 The post-treatment safety assessment will be done 21 ± 7 days after the last dose of study drug.
- 7 All SAEs should be collected from C1D1 until the post-treatment safety assessment. SAEs related or possibly related to study treatment or a study procedure should be reported until the patient is off study. Any death occurring within 30 days after study treatment discontinuation must be reported as an SAE regardless of attribution.
- 8 Appropriate radiographic diagnostic procedures (CT scan of chest, abdomen & pelvis) for evaluation of measurable disease at baseline within 28 days of initiation of the study. CT scans and Chest X-ray will be performed as clinically indicated to follow disease per RECIST 1.1. A confirmation CT scan of response will be performed per RECIST as outlined in the protocol. Patients will be followed for progression every 2 months ± 2 weeks for first year from registration. NOTE: existing scans that are no older than 30 days may be used for the screening scan. RECIST 1.1 Guidelines will be used to evaluate response (see Section 9.0).
- 9 Previous surgical specimens or biopsy samples will be collected for CD30 staining. If none is available, the patient will be offered a repeat biopsy to determine CD30 status.
- 10 Follow up for disease progression and survival will be every 2 months ± 2 weeks for first year from registration. Patients who have progressed will be followed for resolution of all study related toxicity.
- 11 CBC should be done between Day 8 and Day 15 of Cycle 1. This lab can be done locally with results faxed to the study team. Detailed instructions and orders will be provided to patients.
- 12 This will be documented for all patients whenever possible as some patients will not have this information available.

7.1 Screening Evaluations

7.1.1 Within 28 days prior to registration for protocol therapy

- Informed consent
- Study eligibility per inclusion/exclusion criteria
- Medical history and prior disease therapies including ECOG performance status
- Vital signs including height, weight, blood pressure, temperature, pulse and BSA
- Physical examination including testicular examination if appropriate
- Complete blood counts (CBC) with differential
- Chemistry panel (CMP) including serum creatinine, AST, ALT, BUN, phosphate, bilirubin, calcium & magnesium
- Tumor marker measurements including serum alpha-fetoprotein (AFP) and beta human chorionic gonadotropin (BHCG)
- Serum pregnancy test for women of childbearing potential
- Concomitant medication use
- Appropriate radiographic diagnostic procedures (for example CT scan of chest, abdomen & pelvis) for evaluation of measurable disease at baseline within 28 days of initiation of the study. NOTE: Existing scans that are no older than 30 days may be used for the screening scan.
- Previous surgical specimens or biopsy samples will be collected for CD30 staining. If none are available, the patient will be required to do a repeat biopsy to determine CD30 status.

7.2 On Treatment Evaluations

7.2.1 Cycle 1 Day 1

- Complete physical examination including testicular examination if appropriate
- ECOG performance status
- Vital signs including weight, blood pressure, temperature and pulse
- Complete blood counts with differential
- Chemistry panel including serum creatinine, AST, ALT, BUN, phosphate, bilirubin, calcium & magnesium
- Tumor marker measurements including serum alpha-fetoprotein (AFP) and beta human chorionic gonadotropin (BHCG)
- Urine pregnancy test for women of childbearing potential
- Concomitant medication use
- Adverse Event Assessment

7.2.2 Cycle 1 Day 8 (+7 days)

- Complete blood counts with differential

7.2.3 Cycle 2 Day 1 and all subsequent cycles

- Symptom-directed physical examination including testicular examination if appropriate

- ECOG performance status
- Vital signs including weight, blood pressure, temperature and pulse
- Complete blood counts with differential
- Chemistry panel including serum creatinine, AST, ALT, BUN, phosphate, bilirubin, calcium & magnesium
- Tumor marker measurements including serum alpha-fetoprotein (AFP) and beta human chorionic gonadotropin (BHCG)
- Urine pregnancy test for women of childbearing potential
- Concomitant medication use
- Adverse Event Assessment

7.2.4 Before cycle 3 & cycle 5 (D-7 to D1)

- Appropriate radiographic diagnostic procedures (CT scan of chest, abdomen & pelvis) for assessment of response per RECIST 1.1 criteria. Assessments should be the same modality as used for screening.

7.2.5 Before cycle 9 & then after every 4 cycles (D-7 to D1)

- Appropriate radiographic diagnostic procedures (CT scan of chest, abdomen & pelvis) for assessment of response per RECIST 1.1 criteria. Assessments should be the same modality as used for screening.

7.3 Post Treatment Safety Assessment

Subjects discontinued from the treatment phase of the study for any reason will be evaluated 21 days (± 7) after the last dose of study drug. This visit should include the following:

- Complete physical examination
- ECOG performance status
- Vital signs including weight, blood pressure, temperature and pulse
- Complete blood counts with differential
- Chemistry panel including serum creatinine, AST, ALT, BUN, phosphate, bilirubin, calcium & magnesium
- Tumor marker measurements including serum alpha-fetoprotein (AFP) and beta human chorionic gonadotropin (BHCG)
- Serum pregnancy test for women of childbearing potential
- Concomitant medication use
- Adverse Event Assessment

7.4 Long Term Follow-up Evaluations

Patients who achieve a complete remission and are off treatment will be followed every 2 months ± 2 weeks for first year from date of registration. Follow up visits will be done per institutional standard of care. Patients who are discontinued from the treatment for other reasons and are not in remission will be followed for long-term survival and subsequent therapy.

8. BIOSPECIMEN STUDIES AND PROCEDURES

8.1.1 Source and Timing of Biospecimen Collections

Archival tumor tissue will be collected (orchiectomy and metastatic tumor) if available, and a fresh biopsy of tumor if archival tissue is not available will be attempted, for assessment of CD30 expression using immunohistochemistry with anti-CD30 BerH2. All tissues will be sent to the Indiana University Simon Cancer Center Clinical Trials Office Laboratory, [name] where it will be catalogued, and then transferred to the Department of Pathology and Laboratory Medicine at IU Health for IHC by [name]. The CD30 results from the original archival tissue pathology report will also be collected.

Please see Study Procedure Manual for additional processing and shipping information.

8.1.2 Storage of Biospecimens

Any remaining specimens will be stored for future research.

9. CRITERIA FOR DISEASE EVALUATION

Patients will be assessed every cycle by physical examination for response for disease progression and by serum AFP and beta-hCG. Patients will have appropriate radiographic diagnostic procedures (CT scan of chest, abdomen and pelvis) for evaluation of measurable disease at baseline within 28 days of initiation of the study. Imaging can be repeated if required to evaluate the disease (i.e. no elevation of serum tumor markers) before cycle 3, 5 and then every 4 cycles thereafter, at completion of treatment or as clinically indicated. Patients with stable disease or partial or complete response will be eligible for continued therapy.

9.1 The Response Evaluation Criteria in Solid Tumors (RECIST 1.1) will be used as follows:

9.1.1 Measurable disease:

Lesions that can be accurately measured in at least one dimension with longest diameter ≥ 20 mm using conventional techniques or ≥ 10 mm with spiral CT scan.

9.1.2 Malignant lymph nodes:

To be considered pathologically enlarged and measurable, a lymph node must be

>15 mm in short axis when assessed by CT scan (CT scan slice thickness recommended to be no greater than 5 mm). At baseline and in follow-up, only the short axis will be measured and followed.

9.1.3 Non-measurable disease:

All other lesions (or sites of disease), including small lesions (longest diameter

<10 mm or pathological lymph nodes with ≥ 10 to <15 mm short axis), are considered non-measurable disease. Bone lesions, leptomeningeal disease, ascites, pleural/pericardial effusions, lymphangitis cutis/pulmonis, inflammatory breast disease, and abdominal masses (not confirmed and followed by CT or MRI), are considered non-measurable.

Note: Cystic lesions that meet the criteria for radiographically defined simple cysts should not be considered as malignant lesions (neither measurable nor non-measurable) since they are, by definition, simple cysts.

'Cystic lesions' thought to represent cystic metastases can be considered as measurable lesions, if they meet the definition of measurability described above. However, if non-cystic lesions are present in the same patient, these are preferred for selection as target lesions.

9.2 Methods for Evaluation of Measurable Disease:

All measurements should be taken and recorded in metric notation, using a ruler or calipers. All baseline evaluations should be performed within 28 days before the beginning of the treatment.

The same method of assessment and the same technique should be used to characterize each identified and reported lesion at baseline and during follow-up. Clinical lesions will only be considered measurable when they are superficial (e.g., skin nodules and palpable lymph nodes). For the case of skin lesions, documentation by color photography, including a ruler to estimate the size of the lesion, is recommended.

9.3 Methods of Measurement:

CT and MRI are the best currently available and reproducible methods to measure target lesions selected for response assessment. Conventional CT and MRI should be performed with cuts of 5 mm or less in slice thickness contiguously. Spiral CT should be performed using a 5 mm contiguous reconstruction algorithm. This applies to tumors of the chest, abdomen and pelvis. Head and neck tumors and those of extremities usually require specific protocols.

Lesions on chest X-ray are acceptable as measurable lesions when they are clearly defined and surrounded by aerated lung. However, CT is preferable.

Baseline documentation of "Target" and "Non-Target" lesions:

All measurable lesions up to a maximum of 2 lesions per organ and 5 lesions in total, representative of all involved organs, should be identified as **target lesions** and recorded and measured at baseline. Target lesions should be selected on the basis of their size (lesions with the longest diameter), be representative of all involved organs,

but in addition should be those that lend themselves to reproducible repeated measurements. It may be the case that, on occasion, the largest lesion does not lend itself to reproducible measurement in which circumstance the next largest lesion which can be measured reproducibly should be selected. A sum of the diameters (longest for non-nodal lesions, short axis for nodal lesions) for all target lesions will be calculated and reported as the baseline sum diameters. If lymph nodes are to be included in the sum, then only the short axis is added into the sum. The baseline sum diameters will be used as reference to further characterize any objective tumor regression in the measurable dimension of the disease.

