2.2 Endpoints

2.2.1 Primary Endpoint

Objective response (CR + PR) measured by RECIST Criteria v1.1 if there is measurable disease. In case of no measurable disease (marker-only patients), response can be assessed by either a reduction of BHCG by >90% (with no rise in AFP on two

consecutive measures) or a reduction of AFP by >50% (with no rise in BHCG on two consecutive measures).

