5. TREATMENT PLAN

- Eligible patients will be divided into two cohorts, those who are CD30 positive and those who are CD30 negative/unknown. Both groups will be treated similarly and in parallel but analyzed separately.
- CD30 status may be unknown in the unlikely case of tumor-marker-only relapse or when a fresh tumor biopsy is not feasible, and archival tumor tissue is not obtainable

despite efforts to do so. These patients will be included in the CD30 negative cohort for analysis purposes, since statistically NSGCT are more likely to be CD30 negative.

The number of such patients with unknown CD30 status should not exceed 5 patients.

- Enrollment to the study does not have to wait for determination of CD30 status prior to treatment, unless in the situation where one arm is closed for enrollment or an interim assessment of response for the Simon stage I phase is needed. For example:
 - The first 10 patients can enroll on the study and start on therapy without waiting for CD30 status assessment. Prior to enrolling patient number 11, CD30 status need to be determined for all patients to make sure an interim assessment of response for the Simon stage I phase is not needed (i.e. one arm is at 10 patients).
 - If an arm has closed for lack of efficacy, CD30 status need to be assessed prior to starting therapy to make sure that patients belong to the open arm.
 - If both arms advance to the second stage of the Simon design then enrollment can again be pursued without waiting for CD30 status until one arm is closed to accrual.
- Eligible patients will be treated with brentuximab vedotin at 1.8 mg/kg IV every 3 weeks (maximum dose of 180 mg) indefinitely until disease progression, unacceptable toxicity, or study closure.
- Eligible patients with grade 2 peripheral neuropathy at enrollment will be treated with brentuximab vedotin at 1.2 mg/kg IV every 3 weeks (maximum dose of 180 mg) indefinitely until disease progression, unacceptable toxicity, or study closure.
- Response to treatment will be assessed clinically with history, physical exam and tumor markers measurement (BHCG and AFP) on day 1 of each cycle and with CT scans after cycle 2, 4, and every 4 cycles thereafter while receiving treatment.

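### Section 9 makes the scheduled on-treatment scans optional and ties them to marker status, while Sections 5 and 7 schedule CT for every treated patient; partial responses with elevated but stable or falling markers could go unrecorded.

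*Combined protocol and SAP*

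**What the plan says.** Two sets of statements bear on when a treated patient is scanned.

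**Permissive or conditional**
- Section 9, opening paragraph: "Imaging can be repeated if required to evaluate the disease (i.e. no elevation of serum tumor markers". The sentence goes on to name the scans before cycles 3 and 5 and every 4 cycles after that, together with imaging at completion of treatment or on clinical indication. The condition therefore covers the scheduled scans, not only extra ones.
- Section 7, calendar footnote 8: "CT scans and Chest X-ray will be performed as clinically indicated to follow disease per RECIST 1.1". The next sentence of the footnote is firmer: "A confirmation CT scan of response will be performed per RECIST as outlined in the protocol".

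**Scheduled for everyone, no marker condition**
- Section 5: response is assessed "with CT scans after cycle 2, 4, and every 4 cycles thereafter while receiving treatment".
- Section 7 calendar, row "Radiologic evaluations": marked at screening, before cycles 3 and 5, and before cycle 9 and then after every 4 cycles.
- Section 7.2.4, and in the same words 7.2.5: "Appropriate radiographic diagnostic procedures (CT scan of chest, abdomen & pelvis) for assessment of response per RECIST 1.1 criteria".

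**The endpoint that the scans serve.** Section 2.2.1 defines it as "Objective response (CR + PR) measured by RECIST Criteria v1.1 if there is measurable disease"; marker-only response is for patients without measurable disease. Under Sections 9.5 and 12.2.1, partial response needs a fall of at least 30% in the sum of target-lesion diameters, held on repeat measurement, with markers stable or decreasing. Complete response also needs the markers to normalise.

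**The concern.** For a patient with measurable disease and elevated markers, both rules cannot apply. One schedules a scan before cycle 3; the other leaves it to the site and glosses the need for it as the case where markers are not elevated.

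The conflict reaches the primary endpoint because, with measurable disease, no partial response can be recorded without measuring lesions. Section 9 is also where readers are sent: Section 12.6 points there for the response criteria, and calendar footnote 8 cites it for evaluating response. The trial is multicenter, so sites could resolve the conflict differently, and ascertainment would then vary by site and by marker status.

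The decision rule leaves little slack. In each cohort, one response among the first 10 patients separates stopping from continuing, and the fourth response among 29 separates inactive from active. One unrecorded partial response can change either decision. PFS is exposed in the same patients: growth on imaging while markers are stable or falling could be missed or dated late.

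**Working it through.** **1. Who is exposed.** Take a patient with measurable disease and follow Section 9 alone.

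| Marker course | Is a scan called for under Section 9? | Consequence |
|---|---|---|
| Normal, or normalised on treatment | Yes, its stated condition is met | CR or PR can be assessed |
| Confirmed rise of at least 50% from nadir | Not needed | Already progression under Section 9.5 |
| Still elevated, but stable or falling | Not called for | Can satisfy the marker part of PR, but the 30% fall in diameters cannot be shown |

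The third row is the main exposed group. Footnote 8's confirmation CT does not protect it, because a response must first have been seen on a scan.

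**2. Reproduce the plan's figures.** Inputs from Section 12.3: stage 1 of 10 patients, stop at 0 responses; 29 in total, declared active at 4 or more; null rate 0.05, alternative 0.20.

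- Probability of early termination = (1 − p)^10. At p = 0.05: 0.95^10 = 0.5987 (plan 0.599).
- P(active) = sum over x = 1 to 10 of P[Bin(10, p) = x] × P[Bin(19, p) ≥ 4 − x].
- At p = 0.05: 0.0468 (plan 0.047).
- At p = 0.20: 0.2684 × 0.7631 + 0.3020 × 0.9171 + 0.2013 × 0.9856 + 0.1209 (four or more in stage 1) = 0.8011 (plan 0.801).

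All three reproduce.

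**3. Illustration of lost responses.** Suppose a fraction m of true responders lacks the scans needed and stays in the denominator as non-responders. The observable rate is then 0.20 × (1 − m). The value of m is an assumption.

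| m | Observable rate | Power | Chance of stopping at stage 1, (1 − rate)^10 |
|---|---|---|---|
| 0 | 0.20 | 0.801 | 0.107 |
| 5% | 0.19 | 0.768 | 0.122 |
| 10% | 0.18 | 0.730 | 0.137 |
| 20% | 0.16 | 0.640 | 0.175 |

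**4. Direction.** Missed scans remove recorded responses and cannot create them. With a true rate of 5%, the observable rate is at or below 0.05, so the type I error stays at or below 0.047.

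**The case against.** The strongest reply is that the protocol read as a whole already requires these scans. Section 5, the calendar row, 7.2.4 and 7.2.5 all schedule CT without a marker condition, and the last two give RECIST response assessment as the purpose. A site would skip a scan only by preferring one sentence in Section 9 to four schedule entries. Footnote 8 annotates a calendar row with fixed time points, speaks of following disease per RECIST, and requires a confirmation CT. This largely stands. It makes the point an internal contradiction, not a missing assessment schedule. It does not remove the contradiction, since no section is given precedence.

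A reader might infer three stronger things that the documents do not support.

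- *That marker-positive patients with measurable disease will have no RECIST assessment.* Sections 5 and 7 schedule it; the risk arises only where Section 9 is followed instead.
- *That complete responses would be lost as well.* CR requires normal markers, and that is the situation in which Section 9 calls for imaging.
- *That skipped scans shrink the denominator.* Section 12.4 puts every dosed patient in the efficacy population. Section 12.6 limits response evaluability to patients whose disease was re-evaluated but names no modality, and Section 9 has examination and markers every cycle. How an unscanned patient would be counted is unclear, and the tension between 12.4 and 12.6 is a separate matter. If such patients were excluded, the power figures above would not apply.

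**Conclusion.** The point holds as an internal contradiction about how the primary endpoint is ascertained. Section 9 and the general sentence of footnote 8 are permissive; Sections 5, 7, 7.2.4 and 7.2.5 are not. The exposure is mainly possible partial responses in patients with measurable disease whose markers remain elevated but stable or falling, plus late or missed radiologic progression in the same patients.

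The effect, if any, is a lower observed response rate, lower power and a higher chance of a wrong stop at stage 1, with no inflation of the type I error. Its size cannot be derived from the documents. The fall in power to between 0.768 and 0.640 rests on an assumed 5% to 20% of true responders being unscanned and counted as non-responders. It shows sensitivity and does not predict a loss. The wording should be corrected, but the design and its stated operating characteristics are unaffected.

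**What to change.** Reconcile Section 9 and footnote 8 with the schedule already in Sections 5 and 7.

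- **Section 9:** replace the conditional wording with a statement such as: *On-treatment imaging will be repeated at the time points given in Sections 5 and 7 for all treated patients, regardless of serum marker values.* Keep the existing mention of imaging at completion of treatment and of additional imaging when clinically indicated.
- **Calendar footnote 8:** confine the clinical-indication wording to unscheduled scans, and leave the confirmation CT sentence as it is.

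The statement should cover all treated patients, not only those with lesions at baseline. Sections 5 and 7 make no such restriction, and in marker-only patients the appearance of new lesions still defines progression and so PFS.

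The cost is a wording amendment. No scan is added to the existing calendar, and the sample size and decision rules do not change.
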